7.4 Correlative Studies

To support exploratory objectives and correlative studies, blood samples will be collected at the time points indicated on the Schedule of Events. Any blood remaining after completion of the indicated testing will be stored for future unspecified research. With the participant's approval and as approved by the Institutional Review Board (IRB), de-identified biological samples will be stored at Huntsman Cancer Institute's and Intermountain Healthcare Biorepository. These samples could be used to research the causes of cancer, its complications, and other conditions for which individuals with cancer are at increased risk, and to improve treatment.

At the time of consent, subjects will be given the opportunity to opt-out of the use of their samples for future research. During the conduct of the study, an individual participant can choose to withdraw consent to have biological specimens stored for future research. However, the withdrawal of consent with regard to biosample storage may not be possible after the study is completed.

7.4.1 Blood Samples

A blood sample will be obtained from patients to perform duplex DNA sequencing for APC, TP53, KRAS, BRAF, HRAS, and NRAS mutations. Up to 10 mLs of blood will be collected at the time-points indicated on the Schedule of Events and processed to cfDNA. These samples will be used to identify predictive biomarkers for response and resistance.

7.5 Remote Visits/Telehealth

Some study visits and/or procedures may be conducted remotely in the following circumstances:

- Telehealth visits do not present an increased risk to the participant.
- All necessary data for the trial can be collected.
- Procedures do not include research related imaging, lab samples, and/or pathology which should be conducted in person.

Note: The method of telehealth should be documented in the participants' charts.

8 ADVERSE EVENTS

8.1 Definitions

8.1.1 Adverse events

21 CRF 312.32, ICH GCP, and OHRP define an adverse event as any untoward medical occurrence whether or not considered treatment-related. This definition extends to the worsening of any preexisting condition or symptom. All adverse events experienced during trial participation should be documented in the subject's research chart and corresponding eCRF

Laboratory abnormalities should not be listed as adverse events unless deemed clinically significant by the investigator or qualified designee. An abnormal test result or findings should not be recorded as an adverse event unless the following conditions are met:

- Associated with clinical symptoms; and/or
- Requires intervention (medical, surgical, or additional diagnostic testing); and/or
- Results in a change in study drug dosing; and/or
- Deemed by the investigator or qualified designee to be an adverse event.

8.1.2 Serious Adverse Events

A serious adverse event is defined as any untoward event that is:

- Fatal;
- Life-threatening;
- Results in persistent or significant disability/incapacity;
- Medically significant;
- Causes a congenital abnormality or birth defect;
- Requires or prolongs inpatient hospitalization.

Investigator judgment must be used to assess an event as medically significant. The event may not be life-threatening or cause disability but may jeopardize the subject and require intervention to prevent the other SAE outcomes.

The following situations should not be reported as an SAE:

- Hospital admission not associated with a precipitating AE such as:
 - Treatment for a preexisting condition not associated with a new AE or the worsening of a preexisting condition;
 - Admission for social or administrative reasons;
 - Optional admission or elective surgery;
 - Observation;
 - Preplanned treatments or surgical procedures as noted at baseline;
 - Admission for the administration of blood products.

8.2 Adverse Event Reporting

The investigator and qualified designees are responsible for the detection, documentation, reporting, and follow-up of all adverse events experienced by subjects during trial participation. AEs and SAEs will be recorded from the initiation of study therapy until 30 days after last dose of study therapy or until new anti-cancer therapy is started. The following information will be required for each adverse event:

- Event severity as graded by the CTCAE v.5;
- The causality assessment to study medication per the below definitions;

- Expectedness
- Event duration;
- Any action taken to treat or manage the event;
- Event outcome.

8.2.1 Severity Assessment

The severity of adverse events should be assessed by CTCAE v.5. If an event is not listed in CTCAE v.5 then the assessment of severity should follow the general guidelines listed in table 3.

Table 4 : Severity Assessment

Grade	Severity Description
1	Mild event that generally does not require intervention.
2	Moderate event that may require intervention.
3	Severe event that requires intervention.
4	Life-threatening event that requires urgent intervention.
5	Death.

Events meeting grade 4 or 5 severity description should be reported promptly as SAEs unless otherwise indicated in Section 8.1.1

8.2.2 Causality Assessment

The Investigator should assess the causality or relationship of AEs and SAEs to study therapy. The Investigator should consider if there is evidence that the investigational product caused the event taking into consideration timing, organ system affected, type of event, and possible alternative etiologies. The relationship of the AE to study treatment will be reported as listed below. These categories will be defined as follows:

- Definitely related – a clinical event, including laboratory test abnormality, occurring in a plausible time relationship to drug administration, and which cannot be explained by concurrent disease or other drugs or chemicals. The response to the withdrawal of the drug (dechallenge) should be clinically plausible. The event must be definitive pharmacologically or phenomenologically, using a satisfactory rechallenge procedure if necessary.
- Probably related – a reasonable time sequence to the administration of the drug, unlikely to be attributed to concurrent disease or other drugs or chemicals, and which follows a clinically reasonable response on withdrawal (dechallenge). Rechallenge information is not required to fulfill this definition.

- Possibly related – a reasonable time sequence to administrations of the drug, but which could also be explained by concurrent disease or other drugs or chemicals. Information on drug withdrawal may be lacking or unclear.
- Unlikely related –a temporal relationship to drug administration which makes a causal relationship improbable, and in which other drugs, chemicals or underlying disease provide plausible explanations.
- Not related – there is no evidence of a causal relationship between the study drug and the event and in which other drugs, chemicals or underlying disease explain the event.

Adverse events reported as definitely, probably, and possible, related to study therapy will be reported as related. In cases when the Investigator is unsure of the causality of an AE, the event will be considered related to study therapy unless deemed otherwise by the DSMC.

8.2.3 Expectedness

The Investigator will be responsible for determining whether or not an adverse event was expected or unexpected. Expected adverse events are those adverse events that are listed or characterized in the Package Insert (PI) or current Investigator Brochure (IB). Unexpected adverse events are those not listed in the PI or current IB or not identified. This includes adverse events for which the specificity or severity is not consistent with the description in the PI or IB. For example, under this definition, hepatic necrosis would be unexpected if the PI or IB only referred to elevated hepatic enzymes or hepatitis.

8.2.4 Action Taken and Outcome

Start and stop dates will be required for all adverse events and serious adverse events. The action taken in response to the event should also be recorded in the subject's research chart and corresponding eCRF. Event action terms include none, medication administered, non-drug therapy administered, surgery, hospitalization, or other with the option to specify. If a new medication is added the medication should also be added to the concomitant medications log.

All adverse events should be followed until stabilization or resolution. Event outcomes may be classified as resolved, resolved with sequelae, ongoing, or death.

8.2.5 Reporting Serious Adverse Events

All serious adverse events should be reported as soon as possible but no later than one business day after the Investigator becomes aware. All SAEs must be reported on the MedWatch 3500A form and submitted to [contact]. The HCI Clinical Site Monitor will, in turn, submit the MedWatch form to the Medical Monitor. The RCO will summarize and present all reported SAEs according to the Data and Safety Monitoring Plan at the monthly DSMC meeting.

At a minimum, initial SAE reports must include a description of the event, assessment of event causality, event grade, and the expectedness of the event. Although the Investigator may not know all the information at the time of the event, the available information should be reported. An SAE follow-up may be submitted at a later date once more information is known. It is required that follow-up reports be submitted until the SAE is resolved.

The HCI DSMC will notify all participating sites of all unexpected and related SAEs via the Research Compliance Office (RCO). The RCO will also notify all investigators at remote clinical sites participating in a multisite trial of any other safety updates, including external safety reports, manufacturer's reports, and updates to the investigator's brochure.

8.2.5.1 *MedWatch 3500A Reporting Guidelines*

In addition to completing appropriate patient demographic (Section A) and suspect medication information (Section C & D), the report should include the following information within the Event Description (Section B.5) of the MedWatch 3500A form:

- Protocol number and title description
- Description of event, severity, treatment, and outcome if known
- Supportive laboratory results and diagnostics (Section B.6)
- Investigator's assessment of the relationship of the adverse event to each investigational product and suspect medication
- Expectedness of the event (i.e., expected or unexpected event).

Follow-Up Information

It is recommended that follow-up reports be submitted as new information becomes available, however, a follow-up report should be submitted within 7 days of knowledge of event resolution. Additional information may be added to a previously submitted report by any of the following methods:

- Adding to the original MedWatch 3500A report and submitting it as a follow-up
- Adding supplemental summary information and submitting it as follow-up with the original MedWatch 3500A form
- Summarizing new information and faxing it with a cover letter including subject identifiers (i.e. D.O.B. initial, subject number), protocol description and number, if assigned, brief adverse event description, and notation that additional or follow-up information is being submitted (The subject identifiers are important so that the new information is added to the correct initial report)

MedWatch 3500A (Mandatory Reporting) form is available at
<https://www.fda.gov/media/69876/download>

8.2.6 **FDA Notifications**

This study is IND exempted.

8.2.7 **IRB Notification**

The University of Utah IRB requires any unanticipated problems that may increase the risk to research participants be promptly reported. All study-therapy related, unexpected adverse events whose nature, severity, or frequency is not consistent with either:

- The unknown or foreseeable risk of adverse events that are described in the protocol related-documents, such as the IRB-approved research protocol, applicable investigator brochure, the current IRB-approved informed consent document, and/or other relevant sources of information, such as product labeling and package inserts; or
- The expected natural progression of any underlying disease or condition of the subject(s) experiencing the adverse event.

Adverse events meeting this criterion must be promptly reported to the IRB within 10 business days of awareness.

8.2.8 Drug Manufacturer Notifications

- All serious adverse events regardless of relationship to study drug must be reported to Eli Lilly.
- SAE reports should be documented on a MedWatch form and can be faxed or emailed the local safety representative using the following information:
 - Local [contact]
 - Local [contact]
 - Email: [contact]
- Investigator and Institution agree:
 - To provide Lilly with a copy of all information Investigator and/or Institution submit to regulators related to any adverse events for the Study Drug that occur during the Study that Investigator and/or Institution have not otherwise provided Lilly.
 - To notify Lilly, sub-investigators, and the IRB of any problems involving risk to Study patients and report new safety information to IRBs in accordance with applicable requirements;
 - To notify Lilly within fifteen (15) business days of Investigator and/or Institution receiving notification of any “serious” and “unexpected” adverse event experienced by a patient participating in the Study and receiving Study Drug that is possibly related, based on Investigator’s assessment, to the Study Drug.
 - For purposes of this requirement, “serious” means:
 - (1) death;
 - (2) in-patient hospitalization or prolonged hospitalization;
 - (3) life-threatening;
 - (4) persistent or significant disability or incapacity;
 - (5) congenital anomaly or birth defect;
 - or (6) other serious events that may jeopardize the patient and may require medical or surgical intervention to prevent one of the other five listed outcomes and “unexpected” means an adverse drug event that is not consistent with applicable product information in the current labeling for the Study Drug.
 - Serious adverse events should be reported to Lilly using a Medwatch form to Lilly. Investigator and Institution further agree to make available promptly to Lilly such records as may be necessary and pertinent for Lilly to further investigate an

adverse event in the Study that is possibly associated with the Study Drug

8.3 Special Situations

8.3.1 Pregnancy or Breastfeeding

Pregnancy and breastfeeding exposure should be tracked from the start of study therapy until at least 5 half-lives after the last dose of study drug.

Although pregnancy is not considered an adverse event, any exposure to the investigational products during pregnancy or breastfeeding must be reported promptly. Exposure may occur by a woman actively receiving study therapy or the partner of a male subject actively receiving study therapy becomes pregnant. Any possible pregnancy or breastfeeding exposure during study therapy and up to 2 months after the last dose of study therapy or up to the start of subsequent anticancer therapy (whichever happens first) must be reported within one business day of awareness regardless of the occurrence of an SAE. Should a woman on study therapy become pregnant, she should immediately discontinue study treatment.

Women exposed to IP during pregnancy or while breastfeeding will be followed for pregnancy outcome and neonate health. Pregnancy outcomes may meet criteria as an SAE if ectopic pregnancy, spontaneous abortion, intrauterine fetal demise, neonatal death, or congenital anomaly occurs. Congenital anomalies that occur in a live-born baby, a terminated fetus, an intrauterine fetal demise, or a neonatal death should be reported as an SAE. Any neonatal deaths that occur up to 30 days after birth or breastfeeding exposure should be reported as an SAE. Further follow-up on birth outcomes and neonate health will be handled on a case-by-case base.

8.3.2 Hy's Law Cases

It is important to identify possible cases of Drug-Induced Liver Injury (DILI) early. Total bilirubin, AST, and ALT should be regularly monitored for elevations indicative of liver damage. Subjects who experience a transaminase elevation above three times the ULN should be monitored frequently to determine if the elevation is transient. Transient elevations are an indication of adaption and these subjects may be identified as “adaptors.” However, should a transaminase elevation be followed by total bilirubin (TBili) increase, a DILI could be occurring. Any laboratory abnormalities meeting the following criteria should be reported within 24 hours of awareness:

- AST or ALT elevation $> 3 \times$ ULN; and
- Total bilirubin $> 2 \times$ ULN; and
- Absence of cholestasis; and
- No alternative explanation for the elevations (e.g., impaired glucuronidation capacity caused by genetic [Gilbert syndrome]; viral hepatitis A, B, or C, preexisting or acute liver disease; or another drug capable of causing the observed injury).

Investigators should conduct reasonable investigations to rule out other possible etiologies. Investigators should take into consideration the subject's use of ethanol, acetaminophen,

recreational drugs, herbal supplements, and medical history. A potential Hy's Law case will not be considered a confirmed case until all results and considerations have excluded alternative etiologies.

Possible cases of DILI will be promptly reported to the FDA prior to full work up to rule out other etiologies. Reporting should be completed on a MedWatch 3500A form and should include all available information, including the likelihood that the drug caused the event. Subjects should be closely followed until the resolution of the event.

Subjects who experience possible DILI should be managed per the Dose Modification Guidelines.

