6.5 Dose Modifications Guidelines

Subjects experiencing adverse events attributed to study drug may undergo dose modifications for toxicity management. Dose modification guidelines are provided below for adverse events considered to be related to study medication. If either medication requires reduction below Dose Level -3 for toxicity management, study therapy will be discontinued. This study will utilize the CTCAE (NCI Common Terminology Criteria for Adverse Events) Version 5.0 for adverse event and serious adverse event reporting.

Hematological toxicities:

- No cetuximab dose modifications will be made for hematologic toxicity.

Gastrointestinal toxicities:

- No cetuximab dose modifications will be made for diarrhea, mucositis, nausea, or vomiting.

Pulmonary Toxicity

- For grade 2 or worsening pulmonary symptoms unrelated to underlying cancer, cetuximab therapy should be stopped and symptoms investigated. Cetuximab therapy may resume when symptoms resolve to \leq grade 1.
- For \geq grade 3 cough, dyspnea, hypoxia, pneumonitis, or pulmonary infiltrates, skip cetuximab until interstitial lung disease is ruled out. Discontinue all protocol therapy if interstitial lung disease is confirmed.

Hypomagnesemia

- Hypomagnesemia has been seen with cetuximab. Should hypomagnesemia occur, magnesium supplementation should be provided. No dose adjustment is required; however, continue careful monitoring.

Cutaneous Toxicity

- Acne is the most common cutaneous toxicity noted with cetuximab. While there is no clear evidence of benefit, over-the-counter or prescription acne medications designed to treat the acne-like rash may be used for patients who experience the acne-like rash associated with EGFR inhibitors. The investigator could also consider concomitant treatment with topical and/or oral antibiotics; topical corticosteroids are not recommended

Table 2: Cetuximab Dose Delays Due to Cutaneous Toxicity

	Cetuximab	Outcome	Cetuximab dose modification
Grade 3 Rash			
1 st occurrence	Skip infusion 1-2 weeks	If improvement	Continue 500mg/m ²
		If no improvement	Discontinue cetuximab
2 nd occurrence	Skip infusion 1-2 weeks	If improvement	Reduce to 400mg/m ²
		If no improvement	Discontinue cetuximab
3 rd occurrence	Skip infusion 1-2 weeks	If improvement	Reduce to 300mg/m ²
		If no improvement	Discontinue cetuximab
4 th occurrence	Skip infusion 1-2 weeks	If improvement	Reduce to 250 mg/m ²
		If no improvement	Discontinue cetuximab

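### The 24-hour Hy's Law report in Section 8.3.2 is conditional on there being no other explanation, and Section 6.5 has no liver-specific rule and no bar to restart after a confirmed case

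*Combined protocol and SAP*

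**What the plan says.** Section 8.3.2 sets one fixed clock: "Any laboratory abnormalities meeting the following criteria should be reported within 24 hours of awareness". The criteria are joined by *and*: AST or ALT > 3 × ULN, total bilirubin > 2 × ULN, absence of cholestasis, and "No alternative explanation for the elevations". The listed examples of such an explanation include "preexisting or acute liver disease; or another drug capable of causing the observed injury".

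The section also separates potential from confirmed cases. A potential case "will not be considered a confirmed case until all results and considerations have excluded alternative etiologies". On the FDA route it says: "Possible cases of DILI will be promptly reported to the FDA prior to full work up to rule out other etiologies".

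On treatment it says: "Subjects who experience possible DILI should be managed per the Dose Modification Guidelines". Those guidelines are Section 6.5. It covers hematologic, gastrointestinal, pulmonary, magnesium, skin, nail, hypersensitivity and infusion-reaction events, then all other non-hematologic toxicity, then dosing in obesity. Nothing in it names AST, ALT, bilirubin or DILI. The rule for other non-hematologic toxicity of grade 3 or higher is to hold, monitor weekly or more often, and allow restart one dose level lower if the event settles to grade 1 or baseline within 4 weeks. For serious lung events the same section is more specific: "skip cetuximab until interstitial lung disease is ruled out. Discontinue all protocol therapy if interstitial lung disease is confirmed".

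**The concern.** The only fixed deadline in the Hy's Law section depends on a question that the section itself leaves to the later work-up. Patients have metastatic, pretreated disease, and many may have a listed alternative explanation to hand on the day the result is seen, such as liver metastases or another drug. An investigator who follows the wording could wait for the work-up before starting the 24-hour report.

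The second problem is dosing. The referral to Section 6.5 ends in a rule that is keyed to toxicity grade and makes no exception for a confirmed case. Following the written rules, a patient with confirmed drug-induced liver injury who recovers in time may be given cetuximab again. What is at stake is patient safety and consistent handling across the two sites, not the efficacy result.

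**Working it through.** The plan gives no figure to reproduce. The check sets its provisions side by side and adds simple arithmetic.

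**1. The trigger against the definition of a case (Section 8.3.2).** The fourth criterion asks for no alternative explanation. Confirmation asks that all results and considerations have excluded alternatives. The wording differs, but the substance overlaps. The FDA sentence wants possible cases reported before that exclusion is done. So the FDA route has no exclusion test and no fixed limit, while the 24-hour route has a fixed limit and an exclusion test.

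**2. The other reporting routes.**
- FDA (8.3.2): promptly, with no number of days. Section 8.2.6 says only that the study is IND exempt.
- Serious adverse event (8.2.5): one business day. This needs a judgment of seriousness, for which medical significance is enough (8.1.2).
- IRB (8.2.7): 10 business days, if related and unexpected.
- Manufacturer (8.2.8): 15 business days, if serious, unexpected and possibly related.

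None of these is a fixed deadline started by liver values alone.

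**3. Entry limits (Section 5.1, criterion 8) against the numeric trigger.**
- AST/ALT with liver metastases: entry up to 5 × ULN, trigger > 3 × ULN; 5 − 3 = 2 × ULN above the trigger.
- Bilirubin, no Gilbert's: entry up to 2 × ULN, trigger > 2 × ULN; 2 − 2 = 0, so at the limit any rise crosses it.
- Bilirubin, Gilbert's: entry up to 3 × ULN; 3 − 2 = 1 × ULN above the trigger.

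A Gilbert's patient with liver metastases can therefore meet both numeric limits at enrollment. This bears on how the trigger should be rewritten; it does not itself show harm.

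**4. The dosing path.** Under Section 6.5, recovery within 4 weeks (28 days; 28/14 = 2 cycles) permits restart one level down. From the starting dose that is 400 mg/m², and 400/500 = 80% (Table 1). Section 6.3 ends treatment only when a toxicity-related delay exceeds 28 days. The list in Section 6.8.1 has no liver item. No sentence in 6.3, 6.5, 6.8.1 or 8.3.2 bars restart after a confirmed case.

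**5. The lung comparator.** Section 3.2.4 reports interstitial pneumonitis in 3 of 633 patients (3/633 = 0.47%), with one death. Section 6.5 gives it a hold-until-ruled-out and stop-if-confirmed rule. So the protocol does write such rules for rare events.

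**The case against.** The strongest reply is that the fourth criterion can be read as meaning no explanation evident when the result is seen. The clock runs from awareness, and the section keeps potential and confirmed cases apart, so this is a fair reading. It makes the problem an ambiguity rather than an outright contradiction. It does not remove it: the text does not say so, and known liver metastases or a suspect drug would be evident at once.

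The safeguards are also real. A suspected case may well be judged medically significant, which brings the one-business-day clock, notice to the Medical Monitor and monthly DSMC review (8.1.2, 8.2.5, 8.4). Safety laboratory results are reviewed before dosing (7.2.3). Section 8.3.2 adds: "Subjects who experience a transaminase elevation above three times the ULN should be monitored frequently to determine if the elevation is transient". Uncertain causality counts as related (8.2.2), and the investigator may withdraw the patient (6.8.1). These limit the impact, but they rest largely on judgment and none bars restart.

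The lung comparison has limits. Interstitial lung disease is a listed cetuximab toxicity with a reported death, whereas Section 3.2.4 lists no liver toxicity. It serves as a model for wording, not as evidence of equal risk.

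Two stronger readings are tempting and are not supported:
- *If the event is not called serious, the report slips from 24 hours to 10 business days (10/5 × 7 = 14 calendar days, one cycle), so another dose is given first.* The IRB limit is an outer bound on a different notice and does not replace the 24-hour report, whose recipient Section 8.3.2 does not name. A reporting clock does not control dosing, and pre-dose laboratory review applies.
- *Section 6.5 offers nothing for liver events.* The generic rule does hold treatment for a related hepatic event of grade 3 or higher. What is missing is a liver-specific rule tied to the Hy's Law criteria.

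**Conclusion.** The point holds as a cheap improvement. The 24-hour trigger sits badly with reporting possible cases before full work-up and, read literally, can delay the timed report. The management referral leads to a generic, grade-based rule that permits re-exposure after a confirmed case.

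The impact is modest: up to 25 patients, the safeguards above, a restart that is permitted rather than required, and no effect on the sample size or primary analysis. The delay rests on the assumption that an investigator applies the fourth criterion as written and counts liver metastases as preexisting liver disease. The number of cases cannot be sized, because the documents give no frequency of liver injury. Nor do they give CTCAE cut-offs, so it is left open whether a case just above the trigger would reach grade 3 and the generic hold.

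**What to change.** 1. **Section 8.3.2.** Trigger the 24-hour report on AST or ALT > 3 × ULN with total bilirubin > 2 × ULN and no cholestasis. Move the absence of an alternative explanation to the definition of a confirmed case. For any patient enrolled with AST/ALT > 3 × ULN or bilirubin at or above 2 × ULN (liver metastases or Gilbert's), require a stated rise over that patient's own baseline, so that the trigger is not met at entry or by a trivial change. The documents give no figure for that rise and no cut-off for cholestasis; the sponsor should set both.
2. **Section 6.5.** Add, on the model of the interstitial lung disease rule: hold cetuximab when the Section 8.3.2 trigger is met until an alternative cause is established; discontinue permanently if the Hy's Law case is confirmed.

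The cost is amendment wording with IRB approval (Section 10.4). No new tests are needed, since the chemistry panel is already drawn each cycle (Section 1.3). The downside is some extra reports and holds that prove to be disease progression. A hold classed as toxicity-related that runs beyond 28 days would end treatment under Section 6.3, so the amendment should say how such holds are classified.
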